11.1.3. Serious Adverse Events

An SAE is any untoward medical occurrence that, at any dose:

1. Results in death
2. Is life-threatening

NB: An AE is 'life-threatening' if the patient is at immediate risk of death from the event as it occurs (i.e., does not include a reaction that might have caused death if it had occurred in a more serious form). For instance, drug-induced hepatitis that resolves without evidence of hepatic failure would not be considered life-threatening, even though drug-induced hepatitis can be fatal.

3. Requires in-patient hospitalisation or prolongation of existing hospitalisation (see below)
4. Results in persistent or significant disability/incapacity (disability is defined as a substantial disruption of a person's ability to conduct normal life functions)
5. Results in a congenital anomaly/birth defect
6. Results in an important medical event

NB: Important medical events that may not result in death, be life-threatening, or require hospitalisation may be considered SAEs when, based upon appropriate medical

Study Number: SLN360-002	Compound No.: SLN360
Protocol	Version: 1.0

judgement, they may jeopardise the patient and may require medical or surgical intervention to prevent one of the outcomes listed in this definition. Examples of such events are invasive or malignant cancers, intensive treatment in an emergency department or at home for allergic bronchospasm, blood dyscrasias or convulsions that do not result in hospitalisation.

Hospitalisation

Adverse events requiring hospitalisation or prolongation of hospitalisation should be considered serious. In the absence of an AE, the participating Investigator should not report hospitalisation or prolongation of hospitalisation. In general, hospitalisation signifies that the participant has been detained (usually involving at least an overnight stay) at the hospital or emergency ward for observation and/or intervention that would not have been appropriate in the treating physician's office or outpatient setting. Complications that occur during hospitalisation are AEs. If a complication prolongs hospitalisation or fulfils any other seriousness criteria, the event is serious. When in doubt as to whether hospitalisation occurred or was necessary, the AE should be considered serious.

In the following situations, hospitalisation would not qualify as serious:

- Hospitalisation or prolongation of hospitalisation is needed for a procedure required by the protocol

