11.2. Assessment of Adverse Events

11.2.1. Adverse Event Severity

Intensity of all AEs will be graded according to NCI-CTCAE version 5 on a five-point scale (Grade 1 to 5) and reported in detail on the eCRF. Adverse events not listed on the CTCAE should be graded as follows:

- Grade 1: mild; asymptomatic or mild symptoms; clinical or diagnostic observations only; intervention not indicated
- Grade 2: moderate; minimal, local or non-invasive intervention indicated; limiting age-appropriate instrumental activities of daily living (ADL)*
- Grade 3: severe or medically significant but not immediately life-threatening; hospitalisation or prolongation of hospitalisation indicated; disabling; limiting self-care ADL**
- Grade 4: life-threatening consequences; urgent intervention indicated
- Grade 5: death related to AE

*NB: Instrumental ADL refers to preparing meals, shopping for groceries or clothes, using the telephone, managing money, etc.

**NB: Self-care ADL refers to bathing, dressing and undressing, feeding self, using the toilet, taking medications and not being bedridden.

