3.5.1 Adverse Events (AEs)

All AEs will be coded to system organ class and preferred term using MedDRA. Treatment emergent adverse events (TEAEs) are defined as AEs that start after the first dose of study drug. Severity will be graded according to the National Cancer Institute Common Terminology Criteria for Adverse Events (NCI-CTCAE) on a five-point scale (Grade 1 to 5). Study drug-related AEs are defined as AEs considered by the investigator as having a reasonable possibility of being related to study drug.

An overview of TEAEs will be provided including counts and percentages of subjects (and event counts) with the following:

- Any TEAEs (overall and by maximum severity)
- Any study drug-related TEAEs (overall and by maximum severity)
- Any serious adverse events (SAEs)
- Any serious TEAEs
- Any study drug-related serious TEAEs
- Any TEAEs leading to discontinuation of study drug
- Any TEAEs leading to discontinuation of study
- Any TEAEs leading to death

Summary tables of TEAEs, TEAEs by maximum severity, study drug-related TEAEs, serious TEAEs and TEAEs leading to discontinuation of study drug or study will be provided with the number and percentage of subjects with adverse events and the number of events classified by primary system organ class, and preferred term.

System organ classes and preferred terms will be sorted alphabetically.

For tabulations that include classification by relationship to study drug, TEAEs with missing relationship will be considered related to study drug. For tabulations that include classification by severity, missing severity will be considered as the most severe TEAEs that are not SAEs.

Adverse event listings will be presented by subject, system organ class and preferred term.

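### The SAP's rule for missing adverse event severity names no grade and is tied to seriousness, so on its plain wording an ungraded fatal TEAE would be tabulated below Grade 5

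*SAP*

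**What the plan says.** SAP 3.5.1 grades adverse events on the five NCI-CTCAE grades. It tabulates TEAEs and drug-related TEAEs by maximum severity in the overview, and TEAEs by maximum severity within system organ class and preferred term. For these tables, "missing severity will be considered as the most severe TEAEs that are not SAEs". The sentence just before it handles missing causality: "TEAEs with missing relationship will be considered related to study drug". The same overview has rows for SAEs, serious TEAEs and TEAEs that led to death, and none of these needs a grade.

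Protocol 11.2.1 prints a general scale for events that CTCAE does not list. Its top three levels begin "Grade 3: severe or medically significant but not immediately life-threatening", "Grade 4: life-threatening consequences; urgent intervention indicated" and "Grade 5: death related to AE". Protocol 11.1.3 gives "Results in death" as the first seriousness criterion. The second is that the event is life-threatening, explained there as immediate risk of death when the event occurs. Protocol 11.3.1 has severity recorded for each event and, in addition, a classification as serious or non-serious.

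No other text supplies a rule for missing severity. Protocol 12.4.5 leaves imputation to the SAP, and SAP 3.1.8 imputes nothing unless another section says so.

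**The concern.** Severity and seriousness are different attributes, and this rule defines one through the other. It takes the worst level found among events that are not serious and, as written, applies that level to any TEAE without a grade, including serious ones. The neighbouring rule for missing causality is a plain worst case, and SAP 3.1.8 and 3.3.6 also take the most conservative approach to missing dates. The severity rule leaves out the most severe events and gives no reason.

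What is at stake is consistency between safety tables. The overview could count a TEAE that led to death while the maximum-severity display shows nobody at Grade 5. Two programmers could also derive different grades from the same sentence, because it states no grade.

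**Working it through.** The plan gives no figure to reproduce. The check sets the definitions side by side and applies the rule.

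1. **Can a non-serious TEAE be Grade 5?** Grade 5 is death (Protocol 11.2.1) and death is a seriousness criterion (Protocol 11.1.3). So no. This does not depend on which CTCAE term applies.

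2. **Can a non-serious TEAE be Grade 4?** On the general scale Grade 4 means life-threatening consequences, which matches the second seriousness criterion, so the highest non-serious level there is Grade 3. That scale covers only events not listed in CTCAE. Apart from the injection-site scale in Protocol Table 6, the term-specific criteria are not in the documents. A listed term that permits a non-serious Grade 4 would raise the ceiling to 4.

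3. **Apply the rule.** The shortfall is the grade implied by the event's own outcome minus the ceiling:

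| Ungraded TEAE | Grade implied | Ceiling 3 (general scale) | Ceiling 4 (if a listed term allows it) |
|---|---|---|---|
| Fatal | 5 | 5 − 3 = 2 too low | 5 − 4 = 1 too low |
| Life-threatening | 4 | 4 − 3 = 1 too low | 4 − 4 = 0 |

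The fatal case is understated under either ceiling. The life-threatening case is understated only under the first.

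4. **Other ways to program the sentence.** It could mean the highest grade actually observed among non-serious TEAEs. The imputed value would then depend on other participants' data and could fall below the ceilings above. It could also be read as limiting scope: a missing grade counts as most severe, for TEAEs that are not SAEs. Nothing serious is then downgraded, but ungraded SAEs have no rule. On a scale that ends at 5, a non-serious event could also be assigned the grade for death.

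5. **Size.** One affected participant is 1/40 = 2.5% of an SLN360 arm or of the pooled placebo arms, and 1/20 = 5% of a single placebo arm. A participant's maximum is misstated only if no other TEAE of that participant has a recorded grade at least as high as the correct one.

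**The case against.** The best defence is that the sentence is elliptical and was meant to limit scope, so that no serious event is downgraded. Some repair is needed on any reading, since a severity cannot literally be a set of events. But the scope reading needs an added word and has its own two defects, shown above. It changes the fault without removing it.

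The second defence is that the case will hardly arise, and this largely stands. Protocol 11.2.1 requires every adverse event to be graded. Protocol 11.3.2 requires SAE notification within 24 hours and detailed follow-up. A fatal event is among the least likely to reach database lock without a grade. The documents give no rate of missing grades.

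The third defence is that nothing is concealed, and this stands in full. Deaths and serious TEAEs have their own rows, all safety data are listed (SAP 3.5), Protocol 12.4.4.2.1 allows narratives for deaths and for severe or serious events, and safety is not formally tested.

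A reader might infer more than the documents support in two ways. One is that Grade 3 is a firm ceiling for every event, so that every ungraded life-threatening TEAE is understated. That is not established for CTCAE-listed terms. The other is that the level could drop to Grade 2 because hospitalisation appears in the Grade 3 definition and is also a seriousness criterion. That does not follow, because hospitalisation is one of several alternative descriptors and an event can be Grade 3 without it.

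**Conclusion.** The rule needs correcting, as a minor point. On its plain wording an ungraded fatal TEAE is shown below Grade 5, by at least two grades on the general scale or at least one if a listed term permits a non-serious Grade 4. An ungraded life-threatening TEAE may be one grade or more too low, but that rests on the general scale. Under the scope reading, ungraded SAEs have no rule and non-serious events can receive an impossible grade.

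The fatal case assumes only that the sentence applies to all TEAEs, as nothing in it says otherwise. The effect is confined to ungraded TEAEs in the by-severity tables, which should be few. It would be wrong to conclude that deaths or SAEs could go unreported, or that any efficacy result is affected.

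**What to change.** Before database lock and unblinding, replace the sentence in SAP 3.5.1 with:

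*A missing grade is set to 5 if the outcome is fatal, 4 if the event is recorded as life-threatening (eCRF or SAE form), and 3 otherwise; the number of imputed grades is footnoted.*

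This names the grades, gives one derivation and keeps the severity tables in line with the row for deaths. The cost is one sentence and one short piece of programming, with no effect on study conduct or the efficacy analyses.

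There are two small downsides. Protocol 11.3.1 puts outcome and serious/non-serious status on the eCRF but lists no life-threatening item, so that input may have to come from the SAE form. Some mild ungraded events will also be shown as Grade 3, and the footnote makes that visible.

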3.5.2 Clinical Laboratory Tests

Blood samples for clinical laboratory tests will be collected at every scheduled visit and processed by a central laboratory. Urine samples will be analysed locally using a dipstick but may also be analysed centrally if indicated and deemed appropriate by the Investigator. A list of laboratory tests to be performed is specified in the protocol.

Values and changes from baseline will be presented at each scheduled visit and baseline by laboratory test.

Shift tables from baseline to scheduled post-baseline will be tabulated for all laboratory parameters, if applicable.

The number and percentage of subjects with the following potentially clinically significant abnormal liver function tests will be summarized:

- ALT >3xULN
- AST >3xULN
- ALP \geq 2xULN
- Total bilirubin >2xULN
- ALT or AST \geq 3xULN with total bilirubin >2xULN

Both scheduled and unscheduled results will be considered in clinical abnormality laboratory tables.

Listings will list results in Standard International units and conventional units and sort by test, date and time.

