10.2.2. Participant Withdrawal from Study

Participants may withdraw from the study at any time and for any reason without the need for justification. Participants may also be withdrawn by the Investigator if, in the Investigator's opinion, further participation in the study would be deleterious to the participant's health. Reasons for withdrawal could include unacceptable adverse reactions, protocol violation or administrative reasons. To maintain the value and integrity of the study, excessive withdrawals should be avoided where possible.

Where consent remains, every effort must be made to follow-up participants and, other than re-dosing, the scheduled trial assessments should be performed if possible. A reason for withdrawal and an early withdrawal clinic assessments (consisting of assessments included in the Week 36 and EoS visit) as per the Time and Events tables ([Appendix 15.1](#) and [Appendix 15.2](#)) are essential.

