10.2.3. Participant Withdrawal from Investigational Product

A participant will be withdrawn from treatment for any of the following reasons:

- Withdrawal of consent to continue with treatment. The reason for this will be documented if provided
- Lack of compliance, as assessed per the Investigator and/or the Sponsor
- Adverse events that cannot be tolerated by the participant

The reason(s) for withdrawal must be recorded in the eCRF. If a participant is withdrawn from treatment, every effort must be made for the participant to attend scheduled trial assessments if possible. Where a participant withdrawn from treatment is unable to attend scheduled assessments, every effort must be made to have them return for the Week 36 and EoS visits, if possible. Only if the participant is unable to attend scheduled assessments, follow-up may include contact with managing physicians or pharmacists, medical record review and limited phone call visits.

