3.1.2 Analysis Visits

For pharmacodynamics and efficacy parameters, visits will be assigned to analysis visits according to the following visit windows. Within each analysis visit window, scheduled visits will be assigned to analysis visits as recorded on the case report form (CRF). If no scheduled visit is within the analysis visit window, measurement(s) taken at a visit close to the target analysis day will be used as the measurement for that specific visit. Unscheduled visits will not be used unless the scheduled result has not been reported. If samples are collected after the scheduled week 60 analysis these will not be included.

Analysis Visit	Target Analysis Day	Low Analysis Day	High Analysis Day
Screening			
Baseline	1		1
Week 1	8	2	19
Week 4	29	20	43
Week 8	57	44	71
Week 12	85	72	99
Week 16	113	100	127
Week 20	141	128	155
Week 24	169	156	183
Week 28	197	184	211
Week 32	225	212	238
Week 36	252	239	267
Week 40	281	268	309
Week 48	337	310	379
Week 60	421	380	

No study visit window will be used for safety parameters. Analysis visits will be based on the nominal visits as captured on the CRFs.

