3.5.4 Electrocardiograms

For the continuous variables, descriptive statistics of results at each study visit, as well as the change from baseline to each study visit, will be presented in summary tables; for the categorical responses to overall interpretation (rhythm), results and the associated findings at each visit will be summarized by counts and percentages.

Number and percentage of patients with QTcF interval in the categories below will be provided.

- Absolute QTcF interval >500 msec,
- Absolute QT interval >500 msec,
- Increase from baseline QTcF interval >60 msec.

A shift table from baseline to scheduled post-baseline will be tabulated for overall interpretation (rhythm).

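### Laboratory and ECG-rhythm shift tables take scheduled results only, so non-liver abnormalities found off schedule are missing from the by-arm shift summaries

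*SAP*

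**What the plan says.** For laboratory data, SAP 3.5.2 first sets the by-visit summaries: "Values and changes from baseline will be presented at each scheduled visit and baseline by laboratory test". It then defines the shifts: "Shift tables from baseline to scheduled post-baseline will be tabulated for all laboratory parameters, if applicable". SAP 3.5.4 has the matching ECG sentence: "A shift table from baseline to scheduled post-baseline will be tabulated for overall interpretation (rhythm").

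Unscheduled laboratory results are mentioned once: "Both scheduled and unscheduled results will be considered in clinical abnormality laboratory tables". The abnormality criteria listed in that section are five, all hepatic: ALT, AST, alkaline phosphatase, total bilirubin, and ALT or AST together with bilirubin.

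On timing, SAP 3.1.2 says: "No study visit window will be used for safety parameters. Analysis visits will be based on the nominal visits as captured on the CRFs". Pharmacodynamic and efficacy parameters, by contrast, are assigned to visits by study-day windows in the same section.

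Protocol 10.2.2 treats as essential a reason for withdrawal and "early withdrawal clinic assessments (consisting of assessments included in the Week 36 and EoS visit"). Protocol 10.1 also names an early withdrawal visit. That visit has no column in the Time and Events tables, no row in the SAP 3.1.2 window table, and no mention in SAP 3.5.

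**The concern.** Unscheduled tests and withdrawal visits are where an abnormality may be first seen or confirmed. A shift table that excludes them can understate how many participants moved from normal to abnormal, and the shortfall need not be equal across arms.

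For liver tests the SAP has a remedy. For other parameters it has none, although two of the sponsor's own signals lie there. Protocol 1.1.2.2 names the kidney, with the liver, as a toxicological target organ. Protocol 8.2.1 reports transient leukocytosis at 600 mg in Phase 1. This trial does not use 600 mg, but its top dose, 450 mg, was not among the single doses listed in Protocol 1.1.3 (30, 100, 300 and 600 mg). Both documents also justify the sample size partly by a sturdier safety evaluation.

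**Working it through.** The plan states no figure on this point, so the check is mainly textual.

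**1. Where each kind of result goes.** From SAP 3.1.2, 3.4.2 and 3.5 to 3.5.4, and Protocol 6.5.3 and 11.3.1:

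| Result | Shift table | By-visit summary | Abnormality or outlier table | Other routes |
|---|---|---|---|---|
| Liver test, unscheduled | No | No | Yes, five criteria | Listing; AE if clinically significant |
| Renal, haematology, coagulation, other chemistry, unscheduled | No | No | None defined | Listing; AE if clinically significant |
| C-reactive protein, unscheduled | No | As a PD marker, if the scheduled result is missing | None defined | Listing; AE if clinically significant |
| ECG rhythm, unscheduled | No | Planned at each visit; unscheduled tracings not addressed | None defined | Listing; AE if reported |
| QTcF, unscheduled or repeat | None planned | Planned at each study visit; extra tracings not addressed | Categories planned; inclusion not stated | Listing; AE if reported |
| Laboratory result, early-withdrawal visit | Not stated | Not stated | Liver only | Listing; AE if clinically significant |

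The second row is the clear gap: no laboratory summary by arm receives the result. The fourth is narrower, because the rhythm counts by visit do not carry the scheduled-only wording of the shift table.

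**2. Would the next scheduled visit catch it?** Visits fall at Weeks 1, 4 and then every 4 weeks to Week 40, followed by Weeks 48 and 60. The gaps are therefore 3, 4, 8 or 12 weeks. A persistent abnormality would reappear at a scheduled visit if the participant attends; a transient one may not.

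**3. Size per participant.** Inputs: 40 per SLN360 arm and 20 per placebo arm (SAP 2.2.4). Let k be the number of participants in an arm of n whose only abnormal value for a parameter is off schedule, and take all n as the denominator. The shortfall against a table using all results is k/n.

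- SLN360 arm: 1/40 = 2.5 percentage points
- One placebo group: 1/20 = 5.0 points
- Pooled placebo: 1/40 = 2.5 points
- SLN360 arm, assuming k from 1 to 4: 1/40 to 4/40 = 2.5 to 10.0 points

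The documents give no rate from which to choose k. The range is an assumption that shows scale, not a forecast.

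**4. Repeat ECGs.** Protocol 6.5.3 calls for a further ECG when the average QTcF is 500 ms or more. SAP 3.5.4 counts participants above 500 ms without saying whether that further tracing, or any unscheduled one, enters the count.

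**The case against.** The best defence is that the shift tables are one display among several.

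- Protocol 11.3.1 has clinically significant laboratory abnormalities recorded as adverse events. SAP 3.5.1 tabulates treatment-emergent events leading to discontinuation of drug or study, Protocol 12.4.4.2.1 allows narratives, and SAP 3.5 lists all safety data.
- Stopping treatment does not end sampling. Protocol 10.2.3 says: "If a participant is withdrawn from treatment, every effort must be made for the participant to attend scheduled trial assessments if possible". Sections 9.3 and 10.2.2 point the same way.
- Continuous ECG summaries are planned at each study visit, and the QTcF categories carry no scheduled-only limit.
- C-reactive protein is also analysed as a pharmacodynamic marker with day windows, so it is a weak example of the gap.
- Safety output is descriptive, with no formal testing (SAP 3.1.6).

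All of this stands, and it narrows the point without removing it. Adverse event capture depends on a judgement of clinical significance, and Protocol 11.3.1 prefers a diagnosis to a laboratory finding where one can be made. Adverse event tables therefore cannot rebuild a laboratory shift, and listings give no rate by arm.

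Two stronger readings are tempting. A reader might infer that participants stopped for an abnormality will look normal in the safety report. The documents do not support that: such a participant may be missing from a shift table yet counted among discontinuation events, or among the liver abnormalities.

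A reader might also infer that early-withdrawal results will be dropped, or shown under Week 36 or Week 60, so that a Week 8 result would appear 60 − 8 = 52 weeks late. That depends on the CRF label, which neither document gives. Protocol 10.2.2 fixes the content of the visit, not its name, and 10.1 lists it as an alternative to the end-of-study visit. The programming specifications are a separate document (SAP 7). All that can be said is that the SAP is silent. Nor does anything in the SAP mis-time unscheduled results: the shift tables omit them rather than move them.

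**Conclusion.** The point holds for the shift tables. Non-liver laboratory abnormalities and ECG rhythm abnormalities seen only at an unscheduled test are excluded from them by the SAP's wording, and the laboratory ones reach no other laboratory summary by arm. Whether early-withdrawal results share that fate is unresolved, because no rule covers the visit.

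The effect is 2.5 percentage points per affected participant in a 40-participant arm, assuming the whole arm is the denominator and the participant has no abnormal scheduled value for that parameter. How many participants would be affected cannot be estimated from the documents. The efficacy analysis is untouched. This is an inexpensive improvement to descriptive safety output, worth making before database lock.

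**What to change.** Keep the by-visit tables and make three changes to the SAP.

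1. In 3.5.2 and 3.5.4, add a shift from baseline to the worst post-baseline value for every laboratory parameter and for ECG interpretation, using scheduled, unscheduled and early-withdrawal results. Where both low and high values matter, give one shift in each direction.
2. In 3.1.2, state that early-withdrawal safety results are placed by actual study day, using the existing window table. A result on Day 60, for example, would fall in the Week 8 window (Days 44 to 71). If a scheduled result lies in the same window, it takes precedence in the by-visit tables; both still count towards the worst value.
3. In 3.5.4, state that repeat and unscheduled ECGs count in the QTcF categories.

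The cost is SAP wording, minor programming and a few extra tables, with no new visits, samples or participants. Worst-value shifts will show somewhat more abnormalities in every arm, including placebo, so they should be read by comparing arms and alongside the by-visit tables.
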